While approved for dyslipidemia and used off-label for pre-LT PBC and PSC, fibrate safety or efficacy have not been studied in any transplant population for any indication. Additionally, despite the likely benefits (including cost of \$5-25/month), the known risk profile of fibrates, including nephrotoxicity, hepatotoxicity, and myotoxicity, require study in LT recipients who are prone to these toxicities from immunosuppressives and/or their baseline clinical state.

In this prospective pilot study, our primary aim is to describe the tolerability and safety of 12 weeks of once-daily fenofibrate in a LT population, with efficacy as a secondary aim, and determining associations of cholestasis and bile acid activity biomarkers with IC as a tertiary aim.

We believe this pilot study to have at least four key implications on current post-LT care or in opening new areas of investigation. First, demonstrating fenofibrate tolerability and safety early after LT is useful context of IC but also because both PBC and PSC have a 20% recurrence rate after LT and fenofibrate may be considered for post-LT prophylaxis (current standard of care is universal lifelong ursodeoxycholic acid after LT for PBC, and observation alone after LT for PSC). Second, if an efficacy signal is demonstrated, we will leverage the existing three-site Mayo Clinic collaboration (together the largest transplant consortium by far) to conduct a randomized controlled trial to more conclusively assess efficacy of fenofibrate in preventing IC. Third, we hope to determine if biomarkers besides ALP—a test confounded by other liver processes—are associated with IC and facilitate early detection. Fourth, data gathered may allow us to investigate a predictive scoring model utilizing donor and patient characteristics and these biomarkers.

The FICsDCD Study

III. Progress Report and Preliminary Studies

As two of the largest DCD LT program in the nation, the MCA and MCF transplant hepatology teams including this study's PI and Co-Is are experienced in diagnosing and managing IC. Our group holds a monthly DCD IC Multidisciplinary Conference to review cases and discuss management. Finally, the MCA LT Program has contributed to seminal peer-reviewed papers on the DCD IC syndrome including the recently proposed IC classification system.¹ At present we are developing a dataset of over 300 DCD LT recipients at our center which will be used to identify the historical controls of this study.

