- Proportion of patients with elevated serum CK at weeks 4, 8, 12, and post-treatment week 4

Specific Aim 2:

- a. Efficacy: We will use a two-group design to test whether Group 1 (treatment) proportion (P1) is different from Group 2 (control) proportion (P2) ($H_0: P_1 - P_2 = 0$ versus $H_1: P_1 - P_2 \neq 0$). We will use a two-sided, two-sample Fisher's Exact Test with Type I error rate (α) of 0.05.
- b. Sample size: Allowing a 10% dropout rate, a sample size of 32 in the treatment arm and 116 in the historical control arm (1:4 ratio) will achieve 80% power to detect an IC proportion reduction of 30% in the control arm to 5% in the treatment arm.

Specific Aim 3: Serum biomarker association with IC development: We will use the Wilcoxon Rank-Sum test to compare serum ALP, gamma glutamyl transferase, serum BA, FGF19 and 7AC4 levels at weeks 0, 4, 8, and 12 of treatment, with development of IC at 12 of treatment.

Data management: The study will use REDCap, a secure web platform for building and managing online databases and surveys for electronic data collection. REDCap provides automated export procedures for seamless data downloads to Excel and common statistical packages (SPSS, SAS, Stata, R), as well as a built-in project calendar, a scheduling module, ad hoc reporting tools, branching logic, file uploading, and calculated fields.

Schedule of Events

Procedure	Screening: Post-LT day 21-60	Treatment			Post Treatment
		Weeks 0-4	Weeks 5-8	Weeks 9-12	Week 4
Informed consent	X				
Inclusion and exclusion criteria	X				
Physical examination	X				
Medical history	X				
Intervention: fenofibrate		Daily	Daily	Daily	
Routine Labs*	X	Weekly	Weekly	Weekly	Weekly
Study Labs**	X	Once ^{a,b}	Week 6 ^b	Week 12 ^b	Once ^b
Lab result review		Weekly	Weekly	Weekly	Once
Assess tolerability, safety		Weekly	Once	Once	Once

*Protocol transplant monitoring labs (billed to insurance): total bilirubin, ALP, alanine aminotransferase, aspartate aminotransferase, sodium, potassium, creatinine, eGFR, and complete blood count.

**Study labs per FICsDCD budget: GGT, serum bile acids, CK, FGF19 (ELISA), 7AC4 (LC-MS)

^a collect within 3 days after start of treatment

^b combine with transplant monitoring labs

Study Strengths and Limitations:

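### Aim 2 efficacy test: Fisher's exact test is valid and adequately powered, but a two-sided Boschloo test at the same nominal 5% would give a small power gain from the same patients

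*Combined protocol and SAP*

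**What the plan says.** In the combined protocol and SAP, section IV (Research Design and Methods), Analyses, Specific Aim 2, item a sets the hypothesis of equal IC proportions against a two-sided alternative. It begins "We will use a two-sided, two-sample" and names Fisher's "Exact Test with Type I error rate (α) of 0.05".

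Item b gives the size. It opens with "Allowing a 10% dropout rate" and then plans "a sample size of 32 in the treatment arm and 116 in the historical control arm (1:4 ratio"), which "will achieve 80% power" "to detect an IC proportion reduction of 30% in the control arm to 5% in the treatment arm".

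The plan does not give the error rate that Fisher's test actually attains at these sizes, and it mentions neither a mid-p version nor an unconditional exact test. Section II (Background and Significance) describes the study as a pilot "with efficacy as a secondary aim".

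**The concern.** Fisher's test conditions on the total number of IC cases in both groups. This design fixes the group sizes but not that total. With one small group, few tables are possible for any given total, so the largest rejection region with conditional error at or below 5% often falls well short of 5%. Part of the allowed error is then unused, and power is lower than an exact test at the same nominal level could give.

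This matters a little more here than in most pilots. Study Strengths and Limitations names sample size as the main limitation, so power is hard to buy with more patients. Section II makes a later randomized trial conditional on an efficacy signal.

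**Working it through.** **Inputs, all from Specific Aim 2, items a and b.** Two-sided α = 0.05; IC 30% in controls and 5% on treatment; 1:4 ratio; 10% dropout; 32 treated and 116 controls. The 1:4 ratio is exact for 29 treated (29 × 4 = 116), whereas 116/32 = 3.6. I therefore take 29 as the evaluable number and check 32 as well.

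**Step 1: the plan's own figure.** The two-proportion formula with pooled variance under the null and k = 4 has p̄ = (0.05 + 4 × 0.30)/5 = 0.25 and

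n = [1.960 √(1.25 × 0.25 × 0.75) + 0.842 √(0.05 × 0.95 + 0.30 × 0.70/4)]² / 0.25² = 23.6, so 24.

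With the continuity correction,

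n′ = (23.6/4) × [1 + √(1 + 2 × 1.25/(23.6 × 0.25))]² = 28.4, so 29 treated and 116 controls.

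For dropout, 29 × 1.1 = 31.9, so 32 (29/0.9 = 32.2 would round up to 33). The planned size is reproduced. The 80% is the nominal target of an approximate formula, not the exact power of Fisher's test.

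**Step 2: error rates by full enumeration.** Every table is weighted by two independent binomials with a common rate p. The error rate is the total weight of the rejected tables, and its maximum is taken over 1,999 values of p from 0.0005 to 0.9995. Fisher's p-value is the two-sided minimum-likelihood version. Boschloo uses that p-value as its ordering statistic, with the largest cut-off that keeps the maximum error at or below 5%.

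| | 29 v 116 | 32 v 116 |
|---|---|---|
| Fisher, maximum error | 4.06% (p about 0.32) | 4.41% (p = 0.50) |
| Fisher, error at p = 30% | 4.0% | 3.7% |
| Boschloo cut-off on Fisher's p | 0.0582 | 0.0603 |
| Boschloo, maximum error | 4.91% | 4.94% |
| Tables rejected by Boschloo only | 38 | 32 |
| Tables rejected by Fisher only | 0 | 0 |

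**Step 3: power at 29 v 116.**

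| Control v treated IC | Fisher | Boschloo |
|---|---|---|
| 30% v 5% (design) | 87.9% | 90.7% |
| 30% v 10% | 58.6% | 63.9% |
| 30% v 15% | 31.3% | 35.4% |
| 25% v 5% | 72.6% | 74.7% |
| 20% v 5% | 48.6% | 48.9% |
| 15% v 5% | 22.5% | 22.5% |
| 12% v 5% | 10.2% | 10.2% |

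At 32 v 116 and the design rates, power goes from 90.9% to 92.6%.

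**Step 4: where the gain arises.** For 10 to 59 control cases at 29 v 116, the largest treated count that shows benefit differs between the tests only at 32, 33, 34, 47, 48 and 52 control cases. At 32 to 34, Fisher rejects up to 2 of 29 treated cases and Boschloo up to 3. At 35, both reject up to 3. If the control rate is 30%, these six counts together have a probability of about 23%.

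**Step 5: the two-sided definition.** With doubled one-sided p-values at 29 v 116, Fisher has maximum error 3.2% and power 86.8%; Boschloo has 4.8% and 90.7%. The direction is the same, but the figures depend on the definition.

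**The case against.** The strongest reply is that nothing in the plan needs repair. A type I error rate of 0.05 is a ceiling, and Fisher respects it. The sample size reproduces, and exact power exceeds the stated target. On this view, the choice between two valid exact tests is a matter of preference. All of these facts stand, and they limit the point to an optional refinement.

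The reply also notes correctly that the gain depends on the 30% control rate, for which the plan gives no source. Section II quotes 10-12% for DCD recipients at the two centers. The 30% presumably reflects selection on raised alkaline phosphatase. If the true control rate is much lower, power is short under either test and Boschloo adds almost nothing.

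A reader might infer three stronger things that the documents do not support:

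- **That Aim 2 is underpowered because of Fisher.** It is not, at its own design rates: 87.9% against a stated 80%.
- **That the extra power is free.** The nominal 5% limit is unchanged, but the actual maximum false-positive rate rises from about 4.1% to 4.9%. The power comes from spending that slack.
- **That this p-value decides whether the randomized trial goes ahead.** Section II speaks only of an efficacy signal and sets no threshold, and efficacy is a secondary aim.

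What survives is that, at the same nominal level and with the same patients, one exact test rejects in every table where the other does, and in some more.

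**Conclusion.** The point holds as a cheap improvement, not as an error in the plan. At 29 v 116 the gain is 2.7 points of power at the design rates, about 5 points at 30% v 10% and about 2 points at 25% v 5%. It falls to 0.3 points at 20% v 5% and to about zero at control rates of 15% or lower with 5% IC on treatment. These are averages over possible control counts; for any one realized control count the two tests usually set the same cut-off for benefit.

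The figures assume independent binomial outcomes, one common IC rate under the null, 29 (or 32) evaluable treated patients and 116 controls. Neither test protects against bias from comparing treated patients with non-randomized historical controls, and that bias could outweigh a gain of 2 to 3 points.

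**What to change.** In Specific Aim 2, item a, name the two-sided Boschloo exact unconditional test at α = 0.05, ordered by the two-sided (minimum-likelihood) Fisher p-value, as the crude comparison of IC incidence. Keep Fisher's test as a sensitivity analysis.

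Fix the choice before any outcome data are compared, and preferably before the control IC cases are counted. The controls were transplanted between 1/1/2016 and 6/1/2021, so their outcomes may already be on record, and the two cut-offs differ only at certain control counts. The Study Timeline places the historical cohort in months 14-16, which leaves room for this.

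The cost is one sentence in the plan and a few lines of code, with no change in patients, visits or nominal α. The amended text should state that the actual maximum error rises to about 4.9%.

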Fenofibrate to prevent Ischemic
Cholangiopathy in Donation after Circulatory
Death liver transplantation (FICsDCD)

NCT05514119

28October2022

The FICsDCD Study

MEGA Award Protocol

Title of the study:	Fenofibrate to prevent Ischemic Cholangiopathy in Donation after Circulatory Death liver transplantation (FICsDCD)
Principal investigator:	[name]
Co-investigator(s):	[name], [name], [name]
Mentor:	[name]
Statistician:	[name]
IRB# or Activity#	22-007122

Abstract

Ischemic cholangiopathy (IC) is an early-onset, progressive bile duct stricturing syndrome occurring in 5-15% of transplanted livers, leading to biliary obstruction and allograft failure in up to 60% of cases. There is no definitive treatment for IC besides re-transplantation. The differential rate of IC drives the global preference for livers donated after brain death, over more abundant livers donated after circulatory death (DCD) that are prone to warm ischemia—the primary precipitant of IC. Any intervention to ameliorate IC will likely improve DCD organ utilization globally, thereby reducing transplant waitlist mortality and morbidity. Toxic bile acids (BA) in stagnant bile cause bile duct injury and stricturing, which may explain why stricturing progresses even after ischemia resolves at transplantation. Peroxisome proliferator-activated receptor (PPAR) agonists (such as the generic oral agent **fenofibrate**) potently down-regulate BA synthesis, promote BA excretion, and are safe and effective in other cholestatic diseases, but are not studied in transplant recipients. We hypothesize that fenofibrate could be safe, effective, cheap, and thus generalizable to impede the IC propagation. **In this prospective pilot study, we aim to evaluate 1) the tolerability and safety, 2) the efficacy of 12 weeks once-daily fenofibrate in reducing IC incidence after DCD liver transplantation, 3) assess the association between serum markers of cholestasis and development of IC.** Tolerability and safety will be assessed as proportions of: drug discontinuation, and new grade 3 or 4 adverse events. Efficacy will be assessed as incidence of cholangiographically-diagnosed IC and incidence of any IC-related complication.

Research Plan

Specific Aims

Specific Aim 1: To assess the tolerability and safety of 12 weeks once-daily fenofibrate (Lofibra) in a LT recipient population

Primary endpoint: Proportion of patients discontinuing fenofibrate due to adverse events

Secondary endpoints:

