IV. Research Design and Methods

Study design: A single-arm, open-label, prospective study of 12 weeks of fenofibrate (Lofibra) 160mg once daily in donation after circulatory death liver transplant recipients who have serum alkaline phosphatase $>2.5 \times$ ULN 21-60 days after transplantation, to determine fenofibrate tolerability, safety, and efficacy in preventing the ischemic cholangiopathy.

Treatment cohort: Recipients of DCD liver transplants at MCA or MCF

Historical cohort: DCD liver transplant recipients at MCA or MCF between 1/1/2016-6/1/2021

Diagnosis of IC: We will utilize previously-published diagnostic criteria for IC, defined as the occurrence of non-anastomotic biliary strictures in the absence of hepatic artery compromise¹

Inclusion criteria:

1. Female or male patients who have undergone DCD LT
2. At least one serum ALP level $>2.5 \times$ ULN between post-LT days 21-60 days (inclusive) after LT.

Exclusion criteria:

1. LT performed for primary sclerosing cholangitis or primary biliary cholangitis
2. Hepatic artery compromise (e.g thrombosis, stenosis), evaluated on abdominal doppler ultrasonography or angiography prior to enrollment..
3. Untreated biliary anastomotic (surgical) stricture or bile leak between days 0-60 after LT, evaluated during routine clinic examinations, labs, and abdominal ultrasonography.
4. Baseline GFR <30 ml/min
5. Previously known intolerance or allergy to fenofibrate
6. Other clinically significant comorbid condition, including psychiatric conditions, which in the opinion of the study team, may interfere with patient treatment, safety, assessment, or compliance with the treatment
7. Adults lacking capacity to consent to treatment

Interventions:

1. Consenting eligible patients will receive the fenofibrate formulation *Lofibra*, 160mg or renally-adjusted equivalent daily. Intended treatment duration of 12 weeks.
2. Post-transplant laboratory monitoring will be per standard Institutional protocol, at least weekly, through treatment period. Study laboratory monitoring will be done as below.

Analyses:

Specific Aim1:

- a. Tolerability: Proportion of patients who discontinue fenofibrate due to adverse event.
- b. Safety:
 - Proportion of patients with a new grade 3 or 4 adverse events based on CTCAE 5.0 Scale

The FICsDCD Study

- Proportion of patients with acute cellular rejection during fenofibrate treatment
- Mean change in eGFR from baseline at treatment weeks 4, 8, 12, and post-treatment week 4

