The mechanisms of action of PPAR-alpha agonists like fenofibrate predict a strong likelihood of impeding the dreaded transplant complication of IC, yet has not been studied. We propose the first safety and tolerability analysis of fenofibrate in LT recipients. Additionally, we assess the efficacy in reducing IC incidence in a population at increased risk of IC (based on elevated alkaline phosphatase levels at 3-5 weeks after transplant). We proposed fenofibrate as it is readily available and the cheapest PPAR-alpha formulation, at \$5-25/month. Finally, MCA and MCF, as two of the largest DCD LT centers in the nation, makes us uniquely positioned to perform this study, and our existing IC study collaborations in Minnesota and Florida may allow a future multi-center

The FICsDCD Study

randomized controlled trial to more conclusively assess efficacy. Our proposed pilot study is primarily limited by its sample size, owing to a low anticipated IC accrual rate, and the consequent inability to randomize a prospective control arm.

Study Timeline:

Month	0-2	2-4	4-6	6-8	8-10	10-12	12-14	14-16	16-18
Enrolment	X	X	X	X	X				
Treatment	X	X	X	X	X	X	X		
Develop Historical Cohort								X	
Analysis								X	X

V. Human Subjects

Population: The treatment-arm population is 32 adults with decision making capacity, and enrolled from among the MCA and MCF LT recipient population. The control arm is a historical LT recipient population. The study does not involve fetuses, pregnant women, children, prisoners, institutionalized individuals, or others who are likely to be vulnerable.

Research Materials: We will collect, analyze, and biobank blood for study purposes in 32 participants. Participants will receive telephone contact from study coordinators at least monthly during 3 months of treatment, and 1 month after treatment. We will review the electronic medical record of the 32 participants and 116 historical controls including clinical notes, laboratory, imaging, and pathology results, and procedure reports.

Enrolment strategy: Patients who have undergone DCD LT will be screened for eligibility between days 21-60 days after LT. All consecutive LT recipients meeting criteria will be offered enrollment in the study. The historical control cohort will be identified through the Mayo Clinic electronic medical record.

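### The historical controls are scheduled to be assembled and classified for IC only after open-label treatment has ended; the cohort could be built and locked before treated outcomes exist

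*Combined protocol and SAP*

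**What the plan says.** Section IV describes "A single-arm, open-label, prospective study of 12 weeks of fenofibrate" and defines the controls as "DCD liver transplant recipients at MCA or MCF between 1/1/2016-6/1/2021". Specific Aim 2 requires ALP above 2.5x ULN at days 21-60 in both groups, and section IV takes the IC definition from a published classification.

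The sample-size paragraph for Aim 2 gives 32 treated and 116 controls, 10% dropout, a two-sided Fisher test at 0.05 and 80% power "to detect an IC proportion reduction of 30% in the control arm to 5% in the treatment arm". No source is given for the 30%. Section II gives DCD IC rates only for recipients not selected on ALP: 10-30% in general and 10-12% at the two study centres.

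The Study Timeline marks Enrolment to month 10, Treatment to month 14, "Develop Historical Cohort" in months 14-16 only, and Analysis from month 14 to 18. Section V describes how control data are obtained: "We will review the electronic medical record of the 32 participants and 116 historical controls including clinical notes". Section III says that a dataset of more than 300 DCD recipients is now being developed, "which will be used to identify the historical controls of this study". The document is dated "28October2022".

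**The concern.** When a control group is assembled from records after the treated results are in, two steps are exposed to knowledge of those results: which eligible recipients become the 116, and which of them are called IC. The treated arm is open-label, and the documents state no lock date for the controls and no masking of the people who review the charts. Even careful staff would be making borderline calls while knowing how many treated patients developed IC.

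The same schedule leaves the main sizing input, the 30% control rate, unchecked until the study is over. Section II plans a randomized trial if an efficacy signal appears, so the credibility of this comparison matters even though the pilot puts tolerability first, "with efficacy as a secondary aim".

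**Working it through.** **1. Reproduce the stated sample size.** Inputs from Aim 2: p1 = 0.05, p2 = 0.30, two-sided alpha 0.05, power 0.80, k = 4 controls per treated patient. Pooled p = (0.05 + 4 x 0.30)/5 = 0.25.

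- Uncorrected: n' = [1.960 x sqrt(1.25 x 0.25 x 0.75) + 0.842 x sqrt(0.05 x 0.95 + 0.30 x 0.70/4)]^2 / 0.25^2 = (0.949 + 0.266)^2 / 0.0625 = 23.6.
- With continuity correction: n = (n'/4) x [1 + sqrt(1 + 2(k+1)/(k x n' x 0.25))]^2 = 5.9 x (1 + sqrt(1.423))^2 = 28.4, rounded up to 29 treated and 4 x 29 = 116 controls.
- Dropout on the treated arm only: 29 x 1.1 = 31.9, or 32. Conversely, 32 x 0.9 = 28.8, about 29 evaluable.

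The plan's 32 and 116 are reproduced. Exact two-sided Fisher power, summed over both binomials at 29 vs 116, is 87.9%, so the stated 80% is met.

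**2. Could the cohort be built earlier?** The last possible control transplant is 1 June 2021. Adding 60 days (end of the ALP window) and 84 days (a 12-week window, assumed to match the treated cohort) gives 23 October 2021. That is 370 days before the document date of 28 October 2022. On that assumption all control follow-up was complete before the trial began.

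**3. How much does one control classification matter?** For 116 controls and 29 evaluable treated, the largest treated count with two-sided Fisher p <= 0.05 is:

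| Control IC cases of 116 | Largest significant treated count |
|---|---|
| 35-38 | 3/29 |
| 28-34 | 2/29 |
| 22-27 | 1/29 |
| 15-21 | 0/29 |
| 14 or fewer | none (0/29 vs 14/116, p=0.073) |

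At the edges, 2/29 gives p=0.067 against 27 controls with IC and p=0.042 against 28. Likewise 3/29 gives p=0.054 against 34 and p=0.034 against 35. The plan's own expectation is 0.30 x 116 = 34.8 cases, which falls on that last edge. Away from an edge, one reclassified control changes nothing.

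**4. Sensitivity of power to the control rate.** Exact Fisher, 29 vs 116. Control rates below 30% are assumptions, since the documents give none for the ALP-selected population.

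| Control rate | Treated rate fixed at 5% | Plan's relative risk held (0.05/0.30 = 1/6) |
|---|---|---|
| 30% | 87.9% | 87.9% |
| 25% | 72.6% | 78.9% |
| 20% | 48.6% | 63.8% |

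If all 32 treated patients are evaluable, the 25% row becomes 76.5% and 82.5%.

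**The case against.** The best case for leaving the plan alone has four parts.

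- **Much of the control definition is already fixed.** The transplant dates, ALP threshold and window, and published IC definition are all stated. This stands, and it narrows the discretion. What remains open is how 116 are taken from those eligible, how the exclusions and follow-up window are applied in retrospect, and the adjudication of individual charts.
- **The timeline row may mean only final assembly.** The dataset is under way, and someone may look at the rate earlier. That is possible, but no completion date, lock or early check is written down. Section III also places the dataset at one centre while controls come from two, so some work may remain. That argues for starting sooner.
- **Early locking has its own bias.** Open-label assessors who know the control count also know how many treated cases are compatible with significance. This stands as a real cost. It can be limited by identical written criteria and by withholding the count.
- **The stakes are modest.** Efficacy is secondary, and the limitations paragraph already concedes the small sample and the lack of a randomized control arm. This stands and lowers the severity, although that paragraph does not mention the timing of control selection.

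A reader might go further and infer that Aim 2 is underpowered or that 30% is wrong. The documents do not support either. Power on the plan's inputs exceeds 80%, and selection on ALP should raise the rate above the centres' unselected 10-12%. Nor do they equate an efficacy signal with p <= 0.05, so the boundaries above do not decide whether the randomized trial goes ahead.

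**Conclusion.** The point holds as one about schedule and locking. As written, control membership and IC status are settled after open-label treated outcomes are known, and the documents give no reason for the wait. This is an avoidable exposure to bias; it does not show that bias will occur. Its size is set by the Fisher boundaries: near an edge, one control case moves a result across 0.05. Those boundaries assume 29 evaluable treated and exactly 116 controls.

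On sizing, the arithmetic is sound and only the stated basis for 30% is missing. The lower power figures are conditional on assumed control rates, and they depend on whether the treated rate or the relative risk is held. Severity lies between minor and should-fix.

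**What to change.** 1. Move "Develop Historical Cohort" to before first enrolment, or to months 0-2. Before enrolment is cleaner: no treated patient completes 12 weeks before about month 2.8 (84 days), but IC could be diagnosed earlier in treatment.
2. Apply the same ALP window, exclusion criteria, IC definition and follow-up window as for the treated cohort, and state how the 116 are taken if more are eligible.
3. Lock control membership and IC classification, with a recorded date, before treated outcomes are reviewed.
4. Use the same written IC criteria in both groups and, where feasible, keep the control count from those classifying treated patients.
5. State the basis for 30% in the Aim 2 sample-size paragraph. Keep 32 treated. If the locked rate differs materially from 30%, restate power under both a fixed 5% treated rate and a relative risk of 1/6, recomputing if the number of controls is not 116.

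Cost: chart review already planned is done about 14 months earlier, with no added patients, controls, visits or tests. The stated power may become less favourable, and the control rate may become known during treated follow-up, which step 4 limits but does not remove.

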- a. Proportion of patients with a new grade 3 or 4 adverse event.
- b. Proportion of patients with acute cellular rejection during fenofibrate treatment
- c. Mean change in calculated glomerular filtration rate (eGFR) from baseline during fenofibrate treatment weeks 4, 8, 12, and at 4 weeks after end of treatment
- d. Proportion of patients with myopathy confirmed by serum creatine kinase elevation at weeks 4, 8, 12, and at 4 weeks after end of treatment

The FICsDCD Study

Specific Aim 2: To assess IC incidence after 12 weeks of once-daily fenofibrate (Lofibra) in DCD LT recipients, compared with a historical, untreated control. Treatment and control populations will have an elevated predicted risk of IC, defined as alkaline phosphatase >2.5x upper limit of normal (ULN) at 21-60 days after LT.

Primary endpoint: IC incidence with 12 weeks fenofibrate versus a historical untreated cohort.

Secondary endpoints:

- a. Incidence of any IC-related complication at 12 weeks of fenofibrate treatment as a composite endpoint: biliary intervention (biliary stricture dilation, endoscopic biliary stent placement, percutaneous biliary drain placement), initiation of antimicrobial therapy for cholangitis or biloma, re-transplant evaluation due to IC, or death attributed to IC.
- b. Rate of alkaline phosphatase improvement to <1.67x ULN after 12 weeks fenofibrate.

Specific Aim 3: To assess the association between serum biomarkers and IC development.

Endpoints: Correlation of serum alkaline phosphatase, gamma glutamyl transferase, bile acids, fibroblast growth factor 19 (FGF19) and 7-alpha-hydroxy-4-cholesten-3-one (7AC4) levels at weeks 0, 4, 8, and 12 of treatment, with development of IC at 12 weeks of treatment.

II. Background and Significance

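### Aim 3 names 20 unadjusted marker comparisons with no lead marker or week, and the sampling schedule supplies only 12 to 16 of them

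*Combined protocol and SAP*

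**What the plan says.** Section IV, Analyses, Specific Aim 3 plans a "Wilcoxon Rank-Sum test to compare serum ALP, gamma glutamyl transferase, serum BA, FGF19 and 7AC4 levels at weeks 0, 4, 8, and 12" of treatment against IC. The Specific Aims give the same markers and weeks, to be related "with development of IC at 12 weeks of treatment". Neither place states a significance level, a lead marker, a lead week or an adjustment. The only level in the document belongs to Aim 2 ("Exact Test with Type I error rate (α) of 0.05").

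Section II ranks the work as "determining associations of cholestasis and bile acid activity biomarkers with IC as a tertiary aim". It also gives the result a use: "we hope to determine if biomarkers besides ALP" are associated with IC and help early detection, and "data gathered may allow us to investigate a predictive scoring model utilizing donor and patient characteristics and these biomarkers".

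Blood for the markers comes from the treated arm only: "We will collect, analyze, and biobank blood for study purposes in 32 participants" (Section V, Research Materials).

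In the Schedule of Events, ALP is a weekly routine lab. GGT, bile acids, FGF19 and 7AC4 are study labs, taken at screening, once within 3 days of starting treatment, at week 6, at week 12 and once after treatment.

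**The concern.** Twenty separate tests with no stated hierarchy leave the analyst free to report whichever marker and week gives the smallest p-value. Repeated values of one marker in the same patients would count as separate pieces of evidence. Because the plan hopes to use the answer to find early-detection markers and perhaps build a score, a chance finding could be taken as a lead.

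The schedule adds a second problem. Four of the five markers have no sample at two of the four weeks named in Aim 3, so the planned analysis and the planned sampling do not match.

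**Working it through.** **Inputs.** There are 5 markers, 4 weeks and 32 treated patients. The plan's IC rates are 5% treated and 30% control, with 10% dropout (Section IV, Specific Aim 2). Section II gives the two sites' IC rate among all DCD recipients as 10–12%, so 10% serves as a middle case. Assumptions: a two-sided 5% level per test, no ties, no marker truly related to IC, and the correlations shown below.

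**The plan's own figure.** Aim 3 has none. For Aim 2, the continuity-corrected two-proportion formula (5% v 30%, two-sided 5% level, 80% power, 1:4) gives 29 and 116. Then 29 × 1.1 = 31.9, so 32 treated, as stated. I therefore use 29 evaluable treated patients.

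**Number of comparisons.**
- As written in Aim 3: 5 × 4 = 20.
- Supplied by the schedule at the named weeks: ALP × 4, plus 4 markers × 2 (weeks 0 and 12) = 12.
- If week 6 stands in for week 4 or week 8: 4 + 4 × 3 = 16.

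**Simple bound.** With independent tests at exactly 5%, 1 − 0.95^20 = 64%; for 16 tests 56%; for 12 tests 46%.

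**Allowing for the number of IC cases.** Expected cases among 29 are 1.45 at 5%, 2.9 at 10% and 8.7 at 30%.
- 0 cases: no test can be run.
- 1 case: the smallest two-sided exact p is 2/29 = 0.069, so nothing can reach 0.05.
- At a 5% rate, P(0 or 1 case) = 0.95^29 + 29 × 0.05 × 0.95^28 = 0.226 + 0.345 = 57%.
- 2 cases: 18 of the 406 possible rank pairs give p ≤ 0.05, an actual size of 0.0443. Over 20 independent tests, 1 − 0.9557^20 = 60%.

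Averaging over the number of cases at the 5% rate, independent tests: 0.254 × 0.60 (2 cases) + 0.120 × 0.61 (3 cases) + 0.055 × 0.59 (4 or more) ≈ 0.26.

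Simulation of the exact rank-sum test extends this to correlated values. Chance of at least one p ≤ 0.05 in 20 null tests, 29 patients:

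| Treated IC rate | Independent | 0.5 between weeks, 0.3 between markers | 0.7 and 0.5 | 0.9 and 0.7 |
|---|---|---|---|---|
| 5% (planned) | 26% | 22% | 18% | 11% |
| 10% | 48% | 42% | 33% | 21% |
| 30% (no drug effect) | 62% | 54% | 43% | 27% |

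Over the same range of correlations, the comparisons that the schedule can supply give:

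| Treated IC rate | 16 tests | 12 tests |
|---|---|---|
| 5% | 11–22% | 9–18% |
| 10% | 19–42% | 17–34% |
| 30% | 25–54% | 22–44% |

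Simulated entries carry an error of about one percentage point.

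**The case against.** Several arguments count against making much of this.

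- **It is a tertiary aim of a pilot.** Strict family-wise control is not normally asked for at that level, and the protocol names sample size as its main limitation. This stands, and it is why the point is minor. But the plan does not call Aim 3 exploratory or say how a small p-value is to be read.
- **A false positive is not shown to be likely.** A reader might infer that it is, from the 64% bound or by supposing 9 IC cases among 29. The documents do not support that. Thirty per cent is the control-arm rate, the marker samples come from the treated arm, and that arm is planned at 5%. At 5% the chance of 9 or more cases in 29 is about 0.00001.
- **Not every test need be null.** Section II describes elevated ALP as a validated early signal. If ALP is truly associated, the false-positive risk comes from the other four markers and is lower than tabulated.
- **No marker is said to enter the later trial.** A reader might infer that a chance finding would be carried forward. Section II makes the randomized trial conditional on an efficacy signal. It says only that the data may allow a scoring model to be investigated, with no p-value rule for selecting markers.
- **Full correction over 20 tests would be self-defeating.** Bonferroni needs p ≤ 0.05/20 = 0.0025. With 2 cases in 29 the smallest exact p is 2/406 = 0.0049, so at least 3 cases are needed. The chance of 2 or fewer is 82.5% at a 5% rate and 43.5% at 10%. This stands, and that correction is not recommended.

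**Conclusion.** The concern holds in a limited form. Aim 3 lists 20 comparisons without a lead test, level or multiplicity rule, and the schedule cannot supply all of them. On the assumptions above, the chance of at least one false positive over 20 tests is about 11–26% at the planned treated rate, 21–48% at 10% and 27–62% if the drug has no effect. With 12 to 16 tests it is lower but still above 5% in every case examined. The 5% level and the correlations are assumptions, because Aim 3 states neither.

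The larger limit on Aim 3 is the small number of IC cases. No multiplicity rule cures that, and the plan should say so.

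**What to change.** Reword Aim 3 along these lines.

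1. Call it exploratory.
2. Reconcile the weeks named in Aim 3 with the study-lab row of the Schedule of Events.
3. Test each marker once, at one pre-stated time that is the same for cases and non-cases. The week 0 sample is an example that suits early detection.
4. Apply Holm's method over the five tests. Its first threshold is 0.05/5 = 0.01, which 2 cases can reach (0.0049).
5. Report each AUC with a 95% interval and state the number of IC cases.
6. Show the other weeks descriptively, without p-values.

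Avoid averaging each patient's samples up to IC diagnosis. Cases would then contribute fewer and earlier samples, so a null marker that falls on treatment would look higher in cases. In a simulation with 9 cases among 29, within-patient correlation 0.7 and diagnoses spread evenly over visits (all assumed), the false-positive rate per marker was 5% with no trend, 10% with a 1-SD fall and 23% with a 2-SD fall.

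The analysis change costs wording only. Reconciling the weeks is also wording, unless the sponsor chooses to change the draws. The downside is that a marker differing only at a later week is harder to detect. With 0 to 2 IC cases, Aim 3 should be treated as descriptive only.
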